##### **4.3.2. PK Analysis Set**

The PK concentration analysis set is a subset of the safety analysis set and will include patients who have at least one post-dose concentration measurement above the lower limit of quantitation (LLQ) for PF-05082566 or MK-3475.

The PK parameter analysis set is a subset of the safety analysis set and will include patients who have at least one of the PK parameters of interest for PF-05082566 or MK-3475.

##### **4.3.3. Biomarker Analysis Set**

The biomarker analysis set is a subset of the safety analysis set and will include all patients who receive at least one dose of study drug and have baseline and at least 1 on study biomarker assessment.

##### **4.3.4. Immunogenicity Analysis Set**

The immunogenicity analysis set is a subset of the safety analysis set and will include patients who have at least one ADA/Nab sample collected for either PF-05082566 or MK-3475.

## **5. GENERAL METHODOLOGY AND CONVENTIONS**

### **5.1. Hypotheses and Decision Rules**

#### **5.1.1. Hypotheses and Sample Size Determination**

No formal statistical hypothesis testing is planned.

Due to the dynamic nature of the Bayesian allocation procedure, the sample size of the Time-to-Event Continual Reassessment Method (TITE-CRM) cannot be determined in advance. The maximum sample size is set as 45 for dose escalation cohorts in order to have a reliable and accurate estimate of the MTD based on simulation results. Based on probability theory, a sample size of 45 will ensure the estimates of any binary variable (eg, objective response rate) have a 95% confidence interval of width  $<0.30$ . A sample size of 45 also enables the detection of any unexpected toxicity that occurs at 5% rate (in a non-dose-dependent fashion) with a probability of 0.90, and that occurs at 10% rate with a probability of 0.99.

A stopping rule will also be implemented if:

- Maximum sample size ( $n=45$ ) is reached; or
- 9 evaluable patients have been treated at the estimated MTD; or
- All doses appear to be overly toxic and the MTD cannot be determined in the current trial.

Additional patients will be required for expansion cohorts. The total number of patients in expansion cohorts will be determined based on emerging data from this study, cancer indication, and the patient population of interest.

#### **5.1.2. Decision Rules Using the TITE-CRM Method**

The doses of PF-05082566 will be assigned to each enrolled patient using a TITE-CRM method with an adaptive cyclical weight function (Huang and Kuan, 2014), a modified version of the original method proposed by Cheung and Chappell (2000).

Delayed-onset toxicities are a particular challenge for phase I trials of combination therapies. Most of the available dose-escalation designs, including the 3+3 design, the up-and-down designs and the CRM design, require all patients to have completed a fixed observation period for toxicity (eg, 1-2 cycles of the experiment regimen, or 6-8 weeks after start of treatment) before additional cohorts of patients can be enrolled. Thus, trial accrual is patient to opening and closing which may pose logistical risk on the success and completion of the study. In addition, patients who are either lost to follow-up or die of events unrelated to treatment are usually required to be replaced. Due to these reasons, the trial duration could be unacceptably long in case of prolonged observation window and unexpected high rate of patient drop-out.

The time-to-event continual reassessment method (TITE-CRM), a variant of the original CRM method, is open to accrual continually, and maintains other advantages of the CRM relative to the 3+3 design. Like CRM, TITE-CRM seeks to determine the target MTD dose, defined as the dose most closely identified with the target rate, which is the largest acceptable DLT rate determined by the investigators based on the relative costs and benefits of the treatment.

[figure not shown]
TITE-CRM is to be implemented as described by Cheung et al. and Normolle et al. for the dose-escalation of PF-05082566. PF-05082566 may be administered intravenously at the following available dose levels of 0.20, 0.45, 0.9, 1.8, 3.6, and 5 mg/kg on an every 3 week schedule (q3wk). PF-05082566 will be co-administered with MK-3475 on Day 1 of each treatment Cycle. MK-3475 will be administered at 2 mg/kg, MK-3475 will be administered q3wk. Higher dose levels may be available based on the emerging safety data from single agent PF-05082566 dosed at 5 mg/kg in the Phase 1 first-in-human study. The MTD is defined as highest dose that is associated with a DLT rate  $\leq 25\%$ . A power function modeling DLT rate at each dose  $d_i$  ( $i=1, \dots, 6$ ) expressed as  $\Pr(\text{DLT} \mid d_i) = F_i(\beta)$  will be used:

$$F_i(\beta) = p_i^{\exp(\beta)}$$

where  $p_i$  is the prior estimate of DLT rate at dose level  $d_i$ , and  $p_1 \leq p_2 \leq \dots \leq p_6$ . These estimates will be projected based model sensitivity to DLTs, together with single agent safety data for both study drugs.  $\beta$  is an unknown single parameter modeling the dose-toxicity relationship, with prior distribution  $N(0, \sigma_0^2)$ , where  $\sigma_0$  is the standard deviation of the normal prior distribution with mean=0. At the beginning of the trial, the initial prior value of  $\beta$  is set as 0, the prior mean, which gives a prior dose-toxicity model of  $F_i(\beta) = p_i$  based on the power function.

In the Bayesian paradigm, the prior distribution  $N(0, \sigma_0^2)$  expresses the researchers' belief in the quality of the initial estimates  $p_i$ . The smaller the standard deviation  $\sigma_0$ , the more confidence researchers have in the precision of  $p_i$ . and vice versa. As the trial progresses, this prior distribution is combined mathematically with the observed data to yield the posterior distribution of the parameter  $\beta$  (the posterior mean of  $\beta$  will be calculated to model the dose-toxicity relationship). The prior distribution determines how responsive TITE-CRM is to the accumulated data. With a small  $\sigma_0$  upfront, the posterior toxicity probability estimates remain close to the prior estimates unless significantly discrepant data otherwise occur; with a large  $\sigma_0$ , the model will tend to be more immediately responsive to data. In this trial,  $\sigma_0=1$ , which provides a reasonably flat prior distribution of  $\beta$ , with 90% Bayesian credible interval of  $\exp(\beta) : [0.19, 5.21]$ , sufficiently wide to cover a wide spectrum of dose-toxicity scenarios. [Figure 1](#) illustrates the dose-toxicity curve (blue curve) with 90% upper and lower bounds (red curves) when the initial prior estimates  $p_i$  are (0.01, 0.04, 0.08, 0.16, 0.25, 0.35).

**Figure 1. Example Plot of Prior Dose Toxicity Curve**

In the TITE-CRM paradigm, patients who have enrolled in the trial but have not experienced a DLT will be included in the probability calculation with an initial weight equal to the proportion of the 6-week (2 cycles) DLT observation period the patients have completed. However the weight function will be modified if safety data suggest different weight (toxicity) patterns in Cycle 1 and Cycle 2 of PF-05082566. An adaptive cyclical weight function as proposed by Huang et al. (2014) will be implemented.

Patients who experience a DLT or complete the observation period without a DLT will be assigned full weight (=1).

Extensive simulation results comparing the TITE-CRM using the adaptive cyclical weight function with the 3+3 design and other weight functions can be found in Huang et al. (2014).

To avoid overly rapid escalation and to retain the efficiency of dose administration when enrollment is fast, the following restrictions and practical considerations will be followed.

- Dose skipping in escalation to untested doses is not allowed ( $k \rightarrow k+1$ ). In particular, at least three patients should have been treated at dose level  $k$  before escalation to dose level  $k+1$ ;
- At least three patients should have been on treatment (for a minimum of 3 weeks or 1 cycle) and observed DLT rate  $<33\%$  at dose level  $k$  before a patient is assigned to dose level  $k+1$  (*Note that the waiting window depends on our knowledge in the time-to-event pattern of toxicity and accumulating safety data, and thereby the confidence in the associated weights. However, intentional delay in enrollment in the absence of DLT or serious AEs should be minimized and discouraged*);
- Dose escalation recommendation by the TITE-CRM algorithm may be overruled by the sponsor if the nature of the existing data causes safety concern.

## 5.2. General Methods

As described in [Section 3.4](#), in this study ‘**treatment group**’ refers to one of the following:

- Cohort -1: PF-05082566 0.2 mg/kg q3wks + MK-3475 2mg/kg q3wks;
- Cohort 1: PF-05082566 0.45 mg/kg q3wks + MK-3475 2mg/kg q3wks;
- Cohort 2: PF-05082566 0.9 mg/kg q3wks + MK-3475 2mg/kg q3wks;
- Cohort 3: PF-05082566 1.8 mg/kg q3wks + MK-3475 2mg/kg q3wks;
- Cohort 4: PF-05082566 3.6 mg/kg q3wks + MK-3475 2mg/kg q3wks;
- Cohort 5: PF-05082566 5 mg/kg q3wks + MK-3475 2mg/kg q3wks.

Baseline characteristics, disposition and efficacy data will be summarized based on the FAS by treatment group.

DLTs will be summarized based on the DLT-evaluable set by treatment group.

Other safety data, exposure data, concomitant medications and non-drug treatments will be summarized based on the safety analysis set by treatment group.

PK data will be summarized based on the PK analysis set by treatment group.

Biomarker data will be summarized based on the biomarker analysis set by treatment group.

Immunogenicity data will be summarized based on the immunogenicity analysis set by treatment group.

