In addition, once the MTD of PF-05082566 administered in combination with MK-3475 has been estimated with confidence, one or more expansion cohorts of patients with selected advanced solid tumors will be enrolled to further study the safety, tolerability, PK **CCI** and preliminary anti-tumor activity for PF-05082566 in combination with MK-3475 to support RP2D selection, as well as to study tumor-associated biomarkers. The tumor types for further study could include NSCLC and potentially other tumor types based on emerging data from the dose escalation phase of this study.

PK/Anti-Drug Antibody (ADA) sampling will be required for all patients (See [Table 3](#) and [Section 7.2](#) for details). No drug interaction is anticipated between PF-05082566 and MK-3475. Since PF-05082566 and MK-3475 are eliminated via a non-specific catabolic degradation process, it is unlikely that concomitant medication can alter its clearance even if target expression is affected. To assess any potential interactions, steady state pharmacokinetics and the formation of anti-drug antibodies will be monitored for both the agents and compared with historical data.

For all patients in dose-expansion cohorts, a de-novo biopsy will be required at study entry followed by a second biopsy at the time of first follow up scans at 9 weeks (after 3 cycles of treatment). Optional de novo biopsies may be collected for patients in dose-escalation cohorts to support the assessment of disease progression. **CCI**

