### 3.2.2. Efficacy Endpoints

- Objective tumor response by RECIST v1.1;

OR is defined as complete response (CR) or partial response (PR) according to RECIST v1.1 from ‘start date’ until documented disease progression. Both CR and PR must be confirmed by repeat assessments performed no less than 4 weeks after the criteria for response are first met.

- Time-to-response (TTR, expansion cohorts only);

TTR is defined, for patients with an objective response, as the time from the ‘start date’ to the first documentation of objective response (CR or PR) which is subsequently confirmed.

- Duration of response (DR, expansion cohorts only);

DR is defined, for patients with an objective response, as the time from first documentation of objective response (CR or PR) to the date of first documentation of objective progression of disease (PD) or death due to any cause.

- Progression-free survival (PFS, expansion cohorts only);

PFS is defined as the time from ‘start date’ to the date of the first documentation of PD or death due to any cause, whichever occurs first.

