### 3.4. Baseline Variables

#### 3.4.1. Study Drug, Study Treatment and Baseline Definitions

In this study, ‘**study drug**’ refers to PF-05082566 or MK-3475 and ‘**study treatment**’ (or ‘**treatment group**’) refers to one of the following:

- Cohort -1: PF-05082566 0.2 mg/kg q3wks + MK-3475 2mg/kg q3wks;
- Cohort 1: PF-05082566 0.45 mg/kg q3wks + MK-3475 2mg/kg q3wks;
- Cohort 2: PF-05082566 0.9 mg/kg q3wks + MK-3475 2mg/kg q3wks;
- Cohort 3: PF-05082566 1.8 mg/kg q3wks + MK-3475 2mg/kg q3wks;
- Cohort 4: PF-05082566 3.6 mg/kg q3wks + MK-3475 2mg/kg q3wks;
- Cohort 5: PF-05082566 5 mg/kg q3wks + MK-3475 2mg/kg q3wks.

**Start of study treatment** is the first dose of study drug administered.

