#### **4.1. Full Analysis Set**

The FAS will include all patients who receive at least one dose of study drug. Patients will be classified according to the study treatment actually received. If a patient receives more than one treatment the patient will be classified according to the first treatment received.

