##### 6.2.2.1. Objective Response as Assessed by the Investigator per RECIST v1.1

The following analyses will be based on the FAS by treatment group. Assessment of response will be made using RECIST v1.1.

**Best Overall Response (BOR)** will be assessed based on reported overall lesion responses at different evaluation time points from the ‘start date’ until documented disease progression, according to the following rules:

- CR = at least two determinations of CR at least 4 weeks apart and before progression.
- PR = at least two determinations of PR or better at least 4 weeks apart and before progression (and not qualifying for a CR).
- SD (applicable only to patients with measurable disease at baseline) = at least one SD assessment (or better)  $\geq 6$  weeks after ‘start date’ and before progression (and not qualifying for CR or PR).
- Non-CR/non-PD (applicable only to patients with non-measurable disease at baseline) = at least one non-CR/non-PD assessment (or better)  $\geq 6$  weeks after ‘start date’ and before progression (and not qualifying for CR or PR).

- PD = progression  $\leq 12$  weeks after start date (and not qualifying for CR, PR SD, or non-CR/non-PD).
- Not Evaluable (NE): all other cases.

Only tumor assessments performed before the start of any further anti-cancer therapies will be considered in the assessment of BOR. Clinical deterioration will not be considered as documented disease progression.

**Objective Response (OR)** is defined as complete response (CR) or partial response (PR) according to RECIST v1.1 from start date until documented disease progression. Both CR and PR must be confirmed by repeat assessments performed no less than 4 weeks after the criteria for response are first met.

Patients who do not have an on-treatment radiographic tumor assessment (including due to early clinical progression), who receive anti-tumor treatments other than the study treatments prior to reaching a CR or PR, or who die, progress, or drop out for any reason prior to reaching a CR or PR will be counted as non-responders in the assessment of OR. Each patient will have an objective response status (0: no OR; 1: OR). OR rate (ORR) is the proportion of patients with OR in the analysis set.

ORR by treatment group will also be calculated along with the two-sided 95% CI using the Clopper-Pearson method (exact CI for a binomial proportion as computed by default by the FREQ procedure using the EXACT option).

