#### 6.2.2.3. Duration of Response (Expansion Cohort Only)

Duration of Response (DR) is defined, for patients with OR, as the time from first documentation of objective response (CR or PR) to the date of first documentation of objective progression of disease (PD) or death due to any cause. If a patient has not had an event (PD or death), DR is censored at the date of last adequate tumor assessment. The censoring rules for DR are as described below for PFS in [Table 3](#).

$$\text{DR (months)} = [\text{date of event or censoring} - \text{first date of OR} + 1] / 30.4375$$

Kaplan-Meier estimates (product-limit estimates) will be presented by treatment group together with a summary of associated statistics including the median DR time with two-sided 95% CIs. In particular, the DR rate at 3, 6 and 12 months will be estimated with corresponding two-sided 95% CIs. The CIs for the median will be calculated according to [Brookmeyer and Crowley](#) and the CIs for the survival function estimates at the time points defined above will be derived using the log-log transformation according to [Kalbfleisch and Prentice](#) (conftype=loglog default option in SAS Proc LIFETEST) with back transformation to a CI on the untransformed scale. The estimate of the standard error will be computed using Greenwood's formula.

DR will be displayed graphically and analyzed using Kaplan-Meier methodology. If the number of patients with OR is small, the Kaplan-Meier method may not provide reliable estimates. In this case, only descriptive statistics or listings will be provided.

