### 6.4. Subset Analyses

The number of patients expected in each treatment group is small and therefore no subset analyses are planned in this study.

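### Response is tabulated only by PF-05082566 dose, so at the expansion dose the ORR mixes escalation with expansion patients and no expansion cohort has its own planned response estimate

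*SAP*

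**What the plan says.** **Grouping.** SAP 3.4.1 and 5.2 define treatment group as one of six dose levels, from Cohort -1 at 0.2 mg/kg up to "Cohort 5: PF-05082566 5 mg/kg q3wks + MK-3475 2mg/kg q3wks". No group identifies phase, expansion cohort or tumour type.

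**Population.** SAP 4.1: "The FAS will include all patients who receive at least one dose of study drug". Escalation and expansion patients are therefore both in it. SAP 5.2 then sets the efficacy rule: "Baseline characteristics, disposition and efficacy data will be summarized based on the FAS by treatment group".

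**Response.** SAP 6.2.2.1: "ORR by treatment group will also be calculated along with the two-sided 95% CI using the Clopper-Pearson method". BOR is tabulated in the same section. Neither is limited to one phase.

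**Time-to-event endpoints.** SAP 3.2.2 lists "Progression-free survival (PFS, expansion cohorts only", and restricts TTR and DR in the same way. The display unit is still dose. For DR, "Kaplan-Meier estimates (product-limit estimates) will be presented by treatment group", and SAP 6.2.2.5 uses the same rule for PFS.

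**Subsets.** SAP 6.4 cites small expected numbers per treatment group and says "no subset analyses are planned in this study".

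**Purpose of expansion.** Protocol 3.1: "one or more expansion cohorts of patients with selected advanced solid tumors will be enrolled to further study the safety, tolerability". The sentence continues to PK, preliminary anti-tumour activity in support of RP2D selection, and tumour biomarkers. NSCLC is given as a possible tumour type. Protocol 3.6 and 9.3 let tumour type or indication, patient population and emerging data set the number of expansion patients.

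**The concern.** The expansion cohorts are design strata. They are chosen by tumour type, and tumour type also helps to set their size. Their entry rules differ from those of escalation: Protocol 4.1 admits any advanced solid tumour, but criterion 3 additionally requires expansion patients to have tumour accessible for sequential biopsy. The protocol's rationale also expects tumours to differ in T-cell infiltration and PD-L1 expression, and so in likely benefit from PD-1 blockade.

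A response rate that averages over these groups varies with case mix as well as with treatment. Two trials with the same tumour-specific rates but different enrolment would report different ORRs at the same dose. At stake is the readability of the preliminary activity signal that expansion is partly meant to provide. A rate in the selected tumour could be diluted or inflated by the other patients in its row. If the tumour grouping is chosen only after the data are seen, the choice is open to selection.

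**Working it through.** **1. The plan's own precision figure.** Protocol 9.3 and SAP 5.1.1 say that n = 45 gives a 95% interval narrower than 0.30 for any binary variable, naming ORR as an example. The Wald width at p = 0.5 is 2 × 1.96 × √(0.25/45) = 0.292, so the figure reproduces. With Clopper-Pearson, the method the SAP names for ORR, the maximum width is 0.305. The figure describes the escalation maximum taken as one sample. It says nothing about any dose row or expansion cohort.

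**2. Which rows are affected.** Protocol 3.5 sets the expansion dose at the estimated MTD or a lower dose. Rows without expansion patients contain escalation patients only. One stopping criterion (Protocol 3.2, SAP 5.1.1) is 9 evaluable patients at the estimated MTD. If that criterion ends escalation and expansion opens at the MTD, about 9 escalation patients sit in the expansion row.

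**3. Which endpoints are affected.**

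| Endpoint | Patients | Display unit | What is mixed |
|---|---|---|---|
| ORR, BOR | FAS, both phases | Dose | Escalation with every expansion cohort at that dose |
| TTR, DR, PFS | Expansion only | Dose | Expansion cohorts, only if two or more share a dose |

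**4. Size, one expansion cohort.** The documents give no expansion numbers or response rates, so the counts below are assumptions. Intervals are exact (Clopper-Pearson) 95%.

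- Cohort: 8/20 = 40% (19 to 64).
- Escalation at the same dose: 1/9 = 11%.
- Reported row: (8 + 1)/(20 + 9) = 9/29 = 31% (15 to 51).

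The displacement from the cohort's own rate is [9/(9 + n)] × (cohort rate − escalation rate), where n is the cohort size. Holding the rates at 40.0% and 11.1% (a difference of 28.9 points):

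- n = 10: 9/19 × 28.9 = 13.7 points
- n = 20: 9/29 × 28.9 = 9.0 points
- n = 40: 9/49 × 28.9 = 5.3 points

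It is zero if the two rates are equal.

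**5. Size, two cohorts at one dose (assumed counts).**

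- Escalation 0/9.
- Cohort A 6/20 = 30% (12 to 54).
- Cohort B 1/20 = 5% (0 to 25).
- Reported row: (0 + 6 + 1)/(9 + 20 + 20) = 7/49 = 14% (6 to 27).

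A less extreme set, 1/9, 8/20 and 2/20, gives 11/49 = 22% (12 to 37) in place of 40% (19 to 64) and 10% (1 to 32).

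**6. Precision of separate rows.** The widest exact interval is 0.63 at n = 10, 0.52 at n = 15, 0.46 at n = 20 and 0.37 at n = 30.

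**The case against.** The case for leaving the plan alone has several parts.

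- **Descriptive endpoint.** Anti-tumour effect is a secondary objective, Protocol 9.4 promises descriptive summaries only, SAP 5.1.1 plans no hypothesis test, and no rule in either document turns on the pooled ORR. This stands, and it limits the weight of the point.
- **The information is not lost.** Protocol 9.4 lists tumour type, dose and response for each patient. SAP 6.5.1.3 tabulates primary diagnosis by treatment group, and the waterfall plot in SAP 6.2.2.2 is per patient. A cohort rate could be rebuilt by hand. This also stands: what is missing is a planned estimate, not the data.
- **Small numbers.** SAP 6.4 gives this as the reason for no subsets. It is a fair reason not to carve up dose groups after the fact. It is weaker for cohorts that the design itself creates.
- **There may be one cohort only.** Both documents say one or more, and the SAP headings for TTR, DR and PFS use the singular. For those endpoints this answers the concern whenever a dose has a single cohort. It does not answer it for ORR, where escalation patients are still in the row.

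A reader might infer that every dose row is mixed, or that no expansion cohort gets its own PFS estimate. The documents support neither. Expansion is confined to the MTD or a lower dose, and PFS, DR and TTR exclude escalation patients, so a sole cohort at a dose has its own curve. Nor does the pooled rate say nothing about drug effect: it is a weighted average of the group rates and reflects both treatment and case mix.

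**Conclusion.** The point holds for ORR and BOR. At the dose or doses used for expansion, the planned row mixes escalation and expansion patients, and no expansion cohort has a pre-specified response estimate. For TTR, DR and PFS it is conditional: tumour-specific cohorts are merged only if two or more are opened at the same dose.

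The size rests on assumed counts. With 9 escalation patients and rates of 40% and 11%, one cohort of 10 to 40 patients is displaced by about 14 down to 5 points. With two dissimilar cohorts, the single figure can be about half of one rate and nearly three times the other (14% against 30% and 5%). The 9 escalation patients assume that escalation stops on that criterion and that expansion opens at the MTD.

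It would go too far to conclude that the expansion phase cannot serve its purpose. That purpose also covers safety, PK and biomarkers, and patient listings carry tumour type. This is a change that should be made to a descriptive secondary analysis. It does not threaten the primary objective, and no alpha or power is involved.

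**What to change.** - **SAP 3.4.1 and 5.2:** for efficacy, define display groups as (i) escalation patients by dose and (ii) each expansion cohort, identified by tumour type and dose. Dose-level grouping can stay as it is for safety and PK.
- **SAP 6.2.2:** report ORR and BOR for those groups, and TTR, DR and PFS by expansion cohort. Keep the dose-pooled ORR row as a labelled supplement.
- **SAP 6.4:** state that expansion cohorts are planned analysis groups and are not covered by the exclusion of subset analyses.

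The cost is SAP text and table shells, using data already collected. No patients, visits or design features change. The drawback is smaller rows with wider exact intervals, up to about 0.46 wide for a cohort of 20. Where a cohort has few responders, SAP 6.2.2.3 already allows descriptive statistics or listings in place of Kaplan-Meier estimates of DR.
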